4.5.4.3 Nivolumab Dose Reductions and Escalations

There will be no dose escalations or reductions of nivolumab allowed.

4.5.5 Nivolumab Treatment Discontinuation

Nivolumab treatment should be permanently discontinued for the following:

- Any Grade 2 drug-related uveitis or eye pain or blurred vision that does not respond to topical therapy and does not improve to Grade 1 severity within the re-treatment period OR requires systemic treatment
- Any Grade 3 non-skin, drug-related AE lasting > 7 days, with the following exceptions for drug-related laboratory abnormalities, drug-related uveitis, pneumonitis, bronchospasm, hypersensitivity reactions, and infusion reactions:
 - Grade 3 drug-related uveitis, pneumonitis, bronchospasm, hypersensitivity reaction, or infusion reaction of any duration requires discontinuation
 - Grade 3 drug-related endocrinopathies adequately controlled with only physiologic hormone replacement do not require discontinuation
 - Grade 3 drug-related laboratory abnormalities do not require treatment discontinuation except:
 - ◆ Grade 3 drug-related thrombocytopenia > 7 days or associated with clinically significant bleeding requires discontinuation
 - ◆ Any drug-related liver function test (LFT) abnormality that meets the following criteria require discontinuation:
 - AST or ALT > 8 x ULN
 - Total bilirubin > 5 x ULN
 - Concurrent AST or ALT > 3 x ULN and total bilirubin > 2 x ULN
- Any Grade 4 drug-related AE or laboratory abnormality, except for the following events which do not require discontinuation:
 - Grade 4 neutropenia ≤ 7 days
 - Grade 4 lymphopenia or leukopenia
 - Isolated Grade 4 electrolyte imbalances/abnormalities that are not associated with clinical sequelae and are corrected with supplementation/appropriate management within 72 hours of their onset
 - Grade 4 amylase or lipase abnormalities that are not associated with symptoms or clinical manifestations, or radiographic signs of pancreatitis. It is recommended to consult with the BMS Medical Monitor for Grade 4 amylase or lipase abnormalities
 - Grade 4 drug-related endocrinopathy AEs such as adrenal insufficiency, ACTH (Adrenocorticotropic Hormone) deficiency, hyper- or hypothyroidosis, or glucose intolerance, which resolve or are adequately controlled with physiologic hormone replacement (steroids, thyroid hormones) or glucose controlling agents, respectively, may not require discontinuation after discussion with and approval from the BMS Medical Monitor

- Any dosing delay lasting > 6 weeks from the previous dose with the following exceptions:
 - Dosing delays to allow for prolonged steroid tapers to manage drug-related adverse events are allowed. Prior to re-initiating treatment in a subject with a dosing delay lasting > 6 weeks, the BMS medical monitor must be consulted. Tumor assessments should continue as per protocol even if dosing is delayed.
 - Dosing delays > 6 weeks that occur for non-drug-related reasons may be allowed if approved by the BMS medical monitor. Prior to re-initiating treatment in a subject with a dosing delay lasting > 6 weeks, the BMS medical monitor must be consulted. Tumor assessments should continue as per protocol even if dosing is delayed.
- Any adverse event, laboratory abnormality, or intercurrent illness which, in the judgment of the Investigator, presents a substantial clinical risk to the subject with continued nivolumab dosing.
- Disease progression as determined by investigator assessment following the guidelines given in [Appendix 2](#) and [Appendix 4](#) with the exception described in [Section 4.5.9](#).
- Subject who initiated the preparative regimen for allogeneic SCT or ASCT any time after the first dose of nivolumab treatment
- Initiation of antineoplastic therapy (ie, chemotherapy, hormonal therapy, immunotherapy, radiation therapy except for palliative radiation therapy, or standard or investigational agents for treatment of cancer)

Subjects who discontinue nivolumab due to a related AE may continue treatment with brentuximab vedotin monotherapy until disease progression or unacceptable toxicity. The same applies in case subjects discontinue brentuximab vedotin due to related AE and chose to continue on nivolumab monotherapy. During Cohort A, however, if subject meets discontinuation criteria within the DLT evaluation period, both drugs must be discontinued.

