1.1.13.4 Thirty Minute Infusion Time Rationale

Long infusion times place a burden on subjects and treatment centers. Establishing that nivolumab can be safely administered using shorter infusion times of 30 minutes duration in subjects will diminish the burden provided no change in safety profile. Previous clinical studies show that nivolumab has been administered safely over 60 minutes at doses ranging up to 10 mg/kg over

long treatment duration. In Study CA209010, (a Phase 2, randomized, double blinded, dose-ranging study of nivolumab in subjects with advanced/metastatic clear cell RCC) a dose association was observed for infusion site reactions and hypersensitivity reactions (1.7% at 0.3 mg/kg, 3.7% at 2 mg/kg and 18.5% at 10 mg/kg). All the events were grade 1-2 and were manageable. An infusion duration of 30 minutes for 240 mg flat dose of nivolumab (~ 30% of the dose provided at 10 mg/kg) is not expected to present any safety concerns compared to the prior experience at 10 mg/kg nivolumab dose infused over a 60 minute duration.

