3.5 Discontinuation of subjects following any treatment with study drug

Subjects MUST discontinue investigational product (and non-investigational product at the discretion of the investigator) for any of the following reasons:

- Subject's request to stop study treatment
- Any clinical adverse event (AE), laboratory abnormality or intercurrent illness which, in the opinion of the investigator, indicates that continued participation in the study is not in the best interest of the subject
- Termination of the study by Bristol-Myers Squibb (BMS)
- Loss of ability to freely provide consent through imprisonment or involuntarily incarceration for treatment of either a psychiatric or physical (eg, infectious disease) illness
- Additional protocol specific reasons for discontinuation [Section 4.5.5](#) and [Section 4.5.3](#)

In the case of pregnancy, the investigator must immediately notify the BMS Medical Monitor/designee of this event. In most cases, the study drug will be permanently discontinued in an appropriate manner. If the investigator determines a possible favorable benefit/risk ratio that warrants continuation of study drug and it is allowed by local regulations, a discussion between the investigator and the BMS Medical Monitor/designee must occur.

All subjects who discontinue study drug should comply with protocol specified follow-up procedures as outlined in [Table 5.1-3](#). The only exception to this requirement is when a subject

withdraws consent for all study procedures including post-treatment study follow-up or loses the ability to consent freely (ie, is imprisoned or involuntarily incarcerated for the treatment of either a psychiatric or physical illness).

If study drug is discontinued prior to the subject's completion of the study, the reason for the discontinuation must be documented in the subject's medical records and entered on the appropriate case report form (CRF) page.

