4.5.2 Premedication

Routine premedication should not be administered for the prevention of infusion-related reactions prior to the first dose of study drug(s). However, subjects should be carefully monitored for infusion reactions during administration of study drug(s). If an acute infusion reaction is noted, subjects should be managed according to [Section 4.5.6](#).

Subjects should be individually evaluated to assess the need for tumor lysis prophylaxis prior to the first dose of brentuximab vedotin. Subjects should receive prophylaxis as appropriate per the institutional standards.

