4.5.3 Dose Modifications for Brentuximab Vedotin

Table 4.5.3-1 describes the recommended dose modifications for brentuximab vedotin treatment associated toxicity. Doses reduced for brentuximab vedotin-related toxicity should not be re-escalated without discussion with the sponsor. Dose escalation of brentuximab vedotin beyond 1.8 mg/kg is not permitted.

Dose reductions below 1.2mg/kg are not allowed, and toxicities should be managed with dose delays.

If brentuximab vedotin treatment is delayed for any reason, nivolumab must also be delayed until the subject has appropriately recovered and is able to resume the combination treatment on the first day of the subsequent cycle. Nivolumab should only be given alone in case a decision has been made to permanently discontinue brentuximab vedotin.

Table 4.5.3-1: Dose Modifications for Brentuximab Vedotin				
Toxicity	Grade 1	Grade 2	Grade 3	Grade 4
Peripheral Neuropathy	Continue at same dose level	Reduce dose to 1.2 mg/kg and resume treatment ^a	Withhold (delay) until toxicity resolves to ≤ Grade 2 or baseline, then resume treatment at 1.2 mg/kg or discontinue if reduction has already occurred.	Discontinue treatment

Table 4.5.3-1: Dose Modifications for Brentuximab Vedotin				
Toxicity	Grade 1	Grade 2	Grade 3	Grade 4
Non-hematologic (except peripheral neuropathy)	Continue at same dose level	Continue at same dose level	Withhold (delay) dose until toxicity is ≤ Grade 2 or has returned to baseline, then resume treatment at the same dose level ^b	Withhold dose until toxicity is ≤ Grade 2 or has returned to baseline, then reduce dose to 1.2 mg/kg and resume treatment, or discontinue at the discretion of the investigator ^{a,b, c}
Hematologic ^d	Continue at same dose level	Continue at same dose level	Withhold (delay) until toxicity resolves to ≤ Grade 2 or baseline, then resume treatment at the same dose level ^e . Growth factor support (G-CSF or GM-CSF) should be considered for subsequent cycles. If Grade 4 neutropenia recurs despite growth factor support, consider discontinuation or dose reduction to 1.2 mg/kg.	

^a Dose reductions below 1.2 mg/kg are not allowed, and toxicities should be managed with dose delays.

^b Subjects who develop Grade 3 or 4 electrolyte laboratory abnormalities may continue study treatment without dose delay.

^c Treatment should be discontinued for subjects who experience Grade 4 infusion-related reactions.

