4.5.6 Treatment of Infusion Related Reactions (nivolumab/brentuximab vedotin)

Infusion-related reactions may occur during the infusion of study treatment(s). The infusion should be administered at a site properly equipped and staffed to manage anaphylaxis should it occur. All supportive measures consistent with optimal patient care should be given throughout the study according to institutional standards. Supportive measures may include extending the infusion time and/or administering medications for infusion-related reactions.

Infusion or hypersensitivity reactions may occur to either brentuximab vedotin or nivolumab. If such a reaction were to occur, it might manifest with fever, chills, rigors, headache, rash, pruritus, arthralgias, hypotension, hypertension, bronchospasm, or other allergic-like reactions. Infusion reactions should be graded according to NCI CTCAE (Version 4.03) guidelines.

Subjects who experience a Grade 1 or Grade 2 infusion-related reaction should be premedicated for subsequent infusions. Premedication should be given at least 30 minutes prior to dosing study drug(s) and should include an antihistamine and corticosteroid. Recommended doses are: diphenhydramine 25-50 mg IV (or equivalent) and methylprednisolone 40 mg IV (or equivalent). In addition, acetaminophen/paracetamol 325 to 1000 mg and ranitidine 50 mg IV may be given. If the onset of a reaction occurs during an infusion, the infusion may be interrupted for treatment of the infusion-related reaction, including treatment with antihistamines, corticosteroids, and/or bronchodilator therapy, as appropriate. Subjects who experience a Grade 3 infusion-related reaction to brentuximab vedotin or nivolumab may potentially receive additional treatment with the study drug(s) at the discretion of the investigator after discussion with the sponsor.

If anaphylaxis or a Grade 4 infusion-related reaction occurs, administration of the implicated agent(s) (brentuximab vedotin and/or nivolumab) should be immediately and permanently discontinued.

In case of late-occurring hypersensitivity symptoms to nivolumab (eg, appearance of a localized or generalized pruritus within 1 week after nivolumab treatment), symptomatic treatment may be given (eg, oral antihistamine or corticosteroids).

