8.3 Endpoints

8.3.1 Primary Endpoint(s)

The primary safety endpoints include incidence of deaths, adverse events, serious adverse events, adverse events leading to discontinuation, adverse events leading to dose delay, drug-related adverse events and specific laboratory abnormalities (worst grade). Toxicities will be graded using the National Cancer Institute (NCI) Common Terminology Criteria for Adverse Events (CTCAE) version 4.03.

The primary efficacy endpoint is ORR. It is defined as the number of subjects with a best overall response (BOR) of confirmed CR or PR divided by the number of treated subjects. The BOR is defined as the best response designation recorded between the date of first dose and the date of initial objectively documented progression or the date of subsequent therapy, whichever occurs first. Allogeneic SCT and ASCT will be considered as subsequent therapy. In subjects with relapsed refractory DLBCL, relapsed refractory PTCL, relapsed refractory PMBL and relapsed refractory MGZL the response (CR, PR, PD, and progression) will be assessed according to Lugano Classification 2014. For subjects with relapsed refractory CTCL, response will be assessed according to consensus Global Response Score as per the consensus statement of the International Society for Cutaneous Lymphoma. A CR must have been confirmed by scans, including a negative Positron Emission Tomography (PET) to be considered for CR in subjects with PTCL, DLBCL, PMBL and MZGL. In subjects with PTCL, if the bone marrow was compromised at baseline, a bone marrow must also be negative at the time of CR. In CTCL CT scans (chest, neck, abdomen and pelvis), blood flow for SS cells and m SWAT skin scoring along with medical photography will be performed at baseline and at the end of the treatment for response evaluation. The investigator will perform tests that will allow evaluation of response to therapy according to corresponding disease criteria in [Appendix 2](#) and [Appendix 4](#). The analysis of the primary endpoint will occur approximately 8 months after the last enrolled subject's first dose of study therapy. Depending on the enrollment for each disease cohort, the analysis may be done at different times for each cohort, or at the same time for the three cohorts.

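### After a Grade 3 nivolumab infusion reaction, Protocol 4.5.5 requires permanent discontinuation while Protocol 4.5.6 allows further nivolumab

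*Protocol*

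**What the plan says.** Protocol 4.5.5 gives the permanent stopping criteria for nivolumab. Most Grade 3 non-skin, drug-related events require a stop only if they last more than 7 days. That duration test is removed for a short list: "Grade 3 drug-related uveitis, pneumonitis, bronchospasm, hypersensitivity reaction, or infusion reaction of any duration requires discontinuation".

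Protocol 3.5 sets out when subjects must come off investigational product. Its last item, "Additional protocol specific reasons for discontinuation", points to sections 4.5.5 and 4.5.3.

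Protocol 4.5.6 covers infusion reactions to either drug. On Grade 3 it says: "Subjects who experience a Grade 3 infusion-related reaction to brentuximab vedotin or nivolumab may potentially receive additional treatment with the study drug(s", subject to the investigator's decision and a prior discussion with the sponsor. Its permanent stop for the causative drug applies only to anaphylaxis or Grade 4.

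Protocol 4.5.2 tells sites where to look: "If an acute infusion reaction is noted, subjects should be managed according to" section 4.5.6. Section 4.5 gives the same direction. Section 3.4.2.1 also refers to 4.5.6 for premedicated further treatment after an infusion reaction, with no limit on grade.

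**The concern.** For the same drug, event and grade, one section requires a permanent stop and another permits re-exposure. The permissive section is the one sites are told to open when a reaction happens. A clinician who follows it in good faith could give nivolumab again to a subject whom the stopping rule says must not receive it, and would then have a protocol deviation.

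The main stake is subject protection. A secondary one is reporting: Protocol 8.3.1 lists "adverse events leading to discontinuation, adverse events leading to dose delay" among the primary safety endpoints, and the same reaction could end in discontinuation at one site and a resumed dose at another.

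**Working it through.** The plan states no figure on this point, so the check is mainly a comparison of texts.

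| Question | Protocol 4.5.5 with 3.5 | Protocol 4.5.6 |
|---|---|---|
| Drug | Nivolumab | Brentuximab vedotin or nivolumab, both named |
| Grade 3 infusion reaction | Permanent stop, whatever the duration | Further dosing possible |
| Discretion | None for this event | Investigator, after talking to the sponsor |
| Grade 4 | Permanent stop (no exception for infusion reactions) | Permanent stop of the causative drug |
| Cross-reference to the other section on this point | None | None |

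**Can the two be read together?**

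1. *Does the drug wording in 4.5.6 mean only the drug that did not cause the reaction?* The sentence carries no such limit. The next paragraph refers expressly to the implicated drug when that is what it means.
2. *Is 4.5.6 the more specific rule, and so the one that prevails?* Section 4.5.5 is equally specific. It names the event and the grade, and removes the 7-day test for it.
3. *Is 4.5.5 only advisory?* Its opening line is advisory in tone, but the item itself uses the language of requirement and 3.5 is mandatory.
4. *Does the sponsor discussion act as an exception to 4.5.5?* Where 4.5.5 allows a sponsor-level exception it says so, for example for controlled Grade 4 endocrinopathies and for long dosing delays. It gives none for infusion reactions.

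None of these readings removes the conflict.

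**Is brentuximab vedotin affected?** Not in the same way. Table 4.5.3-1 allows resumption after a Grade 3 non-hematologic toxicity has settled, and its footnote c says: "Treatment should be discontinued for subjects who experience Grade 4 infusion-related reactions". Section 4.5.6 is somewhat stricter, because it adds the sponsor discussion and a stop for anaphylaxis, but it forbids nothing that the table requires.

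**Size.** Inputs, from Protocol 8.1: 130 treated in Cohort B, 6 in Cohort A, 40 in B1, 10 in B5. Assumption: a nivolumab-only stop counts as an AE-related discontinuation. One re-dosed subject then changes the rate by 1/n:

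- All treated: 130 + 6 = 136; 1/136 = 0.74 percentage points.
- B1 (DLBCL): 1/40 = 2.5 points. SAP 7.1 pools Cohort A with Cohort B by subtype, so if all 6 Cohort A subjects had DLBCL this becomes 1/46 = 2.2 points.
- B5 (MGZL): 1/10 = 10 points.

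These are effects per case, not expected effects. The documents give no Grade 3 rate. For the earlier nivolumab dose-ranging study, Protocol 1.1.13.4 says of infusion-site and hypersensitivity reactions: "All the events were grade 1-2 and were manageable".

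**The case against.** The strongest reply is that the protocol does show which rule governs stopping. The study design text in Protocol 3.1, the mandatory list in 3.5 and SAP 2.1 all point to 4.5.3 and 4.5.5 for stopping, and none points to 4.5.6. Sections 4.5 and 4.5.2 send sites to 4.5.6 for handling an acute reaction. On this view a mandatory rule outweighs a tentative permission, and the sponsor, which wrote 4.5.5, must be consulted before any re-dosing. Anaphylaxis is stopped under 4.5.6 in any case.

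Much of this is fair, and it narrows the risk. It does not remove it. Section 4.5.6 also contains stopping and re-dosing rules, so a reader sent there has no reason to look further, and the sponsor discussion is framed as a route to more treatment rather than a check against 4.5.5.

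Three smaller points stand:

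- The counting rule for AE-related discontinuations is left to the Core Safety SAP, which is not among the documents. SAP 7.4.2.3 separates stopping all drugs from stopping one, so the point shifts above are conditional.
- Section 4.5.5 also lists Grade 3 hypersensitivity and bronchospasm. Section 4.5.6 covers hypersensitivity reactions to either drug and names bronchospasm as a possible sign.
- In Cohort A, meeting a discontinuation criterion during the DLT period stops both drugs (Protocol 4.5.3 and 4.5.5), and SAP 7.6.1 includes discontinuation for a related AE in its DLT rule. SAP 7.1 describes Cohort A dose exploration in the past tense, so this is probably historical.

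**Conclusion.** The concern holds. For nivolumab, a mandatory safety stopping rule is contradicted by a permission elsewhere in the same protocol, and nothing reconciles them. The conflict is between required and conditionally permitted: stopping complies with both sections, re-dosing does not.

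The number of subjects affected is unknown, probably small and possibly zero. Per re-dosed case, the AE-related discontinuation rate moves by about 0.7 points overall, more in the small cohorts, if nivolumab-only stops are counted. The primary efficacy analysis and its power are not touched. The case for correcting the text rests on subject protection and consistent conduct across sites, not on statistical impact.

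**What to change.** Amend the Grade 3 sentence in Protocol 4.5.6 so that possible further treatment applies to brentuximab vedotin only. State there that a Grade 3 nivolumab infusion reaction ends nivolumab permanently under 4.5.5, with a cross-reference. Pointing to the whole 4.5.5 item would also cover Grade 3 hypersensitivity and bronchospasm. The Cohort A rule that stops both drugs stays as written, and the brentuximab vedotin table needs no change.

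If the sponsor's medical team does want to allow nivolumab again after a Grade 3 reaction, the exception belongs in 4.5.5, with sponsor approval and premedication conditions spelled out. At present 4.5.6 states its premedication rule only for milder reactions: "Subjects who experience a Grade 1 or Grade 2 infusion-related reaction should be premedicated for subsequent infusions".

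The cost is one amended sentence and a cross-reference. No new subjects, assessments or tables are needed.

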4.5.5.1 Management Algorithms for Immuno-Oncology Agents

Immuno-oncology (I-O) agents are associated with AEs that can differ in severity and duration than AEs caused by other therapeutic classes. Nivolumab is considered an immuno-oncology agent in this protocol. Early recognition and management of AEs associated with immuno-oncology agents may mitigate severe toxicity. Management algorithms have been developed to assist investigators in assessing and managing the following groups of AEs:

Gastrointestinal

Renal

Pulmonary

Hepatic

Endocrinopathies

Skin

Neurological

For subjects expected to require more than 4 weeks of corticosteroids or other immunosuppressants to manage an AE, consider recommendations provided in the algorithms. These algorithms are found in [Appendix 6](#) and the Nivolumab IB. Discussions with the BMS Medical Monitor on how to apply these algorithms are strongly encouraged. The guidance provided in these algorithms should not replace the Investigator's medical judgment but should complement it.

